3.4 Eligibility for Cross-over to KW-0761

Subjects who are randomized to the vorinostat arm may cross over to KW-0761 upon progression or in the event of intolerable toxicity (see Section 5.3). Crossover may take place following discussion with the Medical Monitor or designee and receipt of approval for cross over from Kyowa Kirin Pharmaceutical Development, Inc. (KKD). However, they must

continue to fulfill inclusion criteria 6 through 15, and will be excluded if they fulfill the exclusion criteria, except for exclusion criteria 1, 12 and 13 (refer to Section 3.3).

4 INVESTIGATIONAL PLAN

4.1 Overview of Study Design

This is an open-label, multi-center randomized, Phase 3 study with 1:1 randomization of study drug, KW-0761 versus the comparator, vorinostat.

4.2 Number of Subjects

Approximately 317 subjects may enroll in this study over a period of 24 months. The primary analysis will be conducted when 255 total progression-free survival (PFS) events have been observed or 24 months after the last randomized subject's first dose, whichever comes first.

4.3 Investigational Centers

It is anticipated that approximately 75 investigational centers in the US, Europe, Japan and Australia will participate in this study.

5 TREATMENT PLAN

5.1 Assignment to Study

After a subject signs consent, screening numbers should be assigned by the investigator (or designee) using ClinTrak Interactive Voice/Web Response System (CTIVRS). Once assigned, numbers for any screen failures or non-treated, non-evaluable, or discontinued subjects will not be re-used.

A subject who meets all entry criteria will be randomized in a 1:1 ratio to receive KW-0761 or vorinostat. The randomization to treatment groups will be stratified by disease type (MF or SS) and disease stage (IB/II or III/IV). When a subject is determined to be eligible for randomization the investigator (or designee) will contact CTIVRS to obtain the randomization assignment for the subject. If a subject is randomized in error, or a dosing error occurs, KKD (or designee) should be notified as soon as the error is discovered.

5.2 Study Treatments

In this protocol, study treatments are KW-0761 and vorinostat. Subjects will be randomized to the study drug, KW-0761 or comparator, vorinostat, in a 1:1 ratio.

5.2.1 Study Drug: KW-0761 (mogamulizumab)

Treatment can be administered on an outpatient basis. Subjects will receive 1.0 mg/kg of KW-0761 as an iv infusion over at least 1 hour on Days 1, 8, 15, and 22 of the first cycle and on Days 1 and 15 of subsequent cycles. No other investigational or commercial agents or therapies other than the study treatment and those described in Section 5.4.1 may be administered with the intent to treat the subject's malignancy.

5.2.1.1 Premedication Prior to KW-0761 Infusion

It is recommended that subjects be premedicated with acetaminophen or paracetamol orally and diphenhydramine 50 mg iv (or equivalent anti-histamine) before the first KW-0761 infusion. For subjects who experience an infusion related reaction, premedication is recommended prior to every subsequent infusion.

5.2.1.2 Definition of Treatment Cycle

Each treatment cycle is 28 days.

5.2.1.3 Delays in Dosing

During the first treatment cycle, KW-0761 should be administered beginning on Day 1 and within ± 2 days of the other scheduled visits (i.e., Days 8, 15 and 22 during Cycle 1; Day 15 during subsequent cycles). If the study visit does not occur within this visit window, KW-0761 should not be administered at the visit and the next dose should be administered at the next timepoint.

A subject's next cycle should begin within 2 weeks of the completion of the prior cycle. The start of a new cycle may be delayed to allow resolution of treatment-related toxicities or for non-medical reasons (holidays, vacations, etc.). Delay of the start of a new cycle greater than 2 weeks must be discussed with the Medical Monitor or designee.

5.2.1.4 Duration of Treatment

Subjects may remain in the treatment phase up until PD, drug intolerance or unacceptable toxicity, or until any of the other criteria for study removal are met, as defined in Section 5.5. Except in cases of unacceptable toxicity or drug intolerance, every effort should be made to ensure the subject remains in the study until disease progression (See Section 7.2.4, regarding definition of disease progression).

At each cycle, the investigator must minimally have reviewed the modified Severity Weighted Assessment Tool (mSWAT) to determine if progression of skin disease has

occurred prior to subsequent dosing. Ideally, results of flow cytometry and CT assessment, as applicable, should be reviewed at this visit as well. However, it is understood that these results may not be reported for several days and may not be available. Once those results are obtained evidence of progression in all compartments should be determined.

In cases where the definition of PD or relapse is met but the clinical impression is questionable, subjects may remain on study until the next evaluation (4 weeks later if questionable finding in skin or blood; 8 weeks later in first year and 16 weeks later after Year 1 if questionable finding in lymph nodes or viscera, with at least stable disease in other compartments) to avoid a subject being removed prematurely from the study. If PD is confirmed at this subsequent evaluation, subject should be discontinued from treatment. If PD is not confirmed at this subsequent evaluation, the subject may remain on study.

This course of action only applies to cases where the clinical impression is questionable; subjects in frank or obvious PD in any compartment should be discontinued from protocol therapy.

If clinical progression is noted at any time prior to the scheduled assessments for efficacy, the assessments (computed tomography [CT], mSWAT, skin photographs and flow cytometry) should be done at that time to fully document disease progression. CT must be performed even if previously negative at baseline.

If the subject experiences an overall CR, the subject may continue treatment for up to 12 months or until progression, whichever comes first.

For subjects who are continuing to receive study treatment at the time of the primary efficacy analysis, procedures and assessments are described in Section 7.7. Procedures to be followed for subjects who are continuing to receive KW-0761 at the time of initial marketing authorization are described in Section 7.8.

5.2.1.5 Replacement of Subjects

Subjects will not be replaced.

5.2.1.6 Dose Modifications

No dose modifications of the KW-0761 will be permitted in this study.

5.2.1.7 Treatment of Hypersensitivity-Like Reactions

It may be difficult to differentiate an infusion reaction from a true hypersensitivity (i.e., allergic) reaction. If a reaction occurs during infusion of KW-0761, investigators may use the following guidelines to best treat the subject's symptoms:

Grade 1/2:

- Stop the infusion for 15–30 minutes;
- Acetaminophen or paracetamol orally and diphenhydramine 50 mg iv or equivalent anti-histamine may be administered;
- If symptoms abate, re-start the infusion at one-half the previous rate;
- If symptoms do not abate after 30 minutes, discontinue that day's treatment. Additional medical measures, such as administration of corticosteroids (see below) may be considered for reactions that do not abate after 30 minutes.

Grade 3

- Stop the infusion for 15–30 minutes;
- Consider administering the following:
 - Acetaminophen or paracetamol orally;
 - Diphenhydramine 50 mg iv or an equivalent anti-histamine;
 - Dexamethasone 20 mg iv or an equivalent corticosteroid;
 - Albuterol or salbutamol inhaler 2 puffs p.r.n. for bronchospasm or an equivalent bronchodilator;
 - O₂ by nasal cannula.
- Additional agents may be administered per institutional guidelines for the treatment of infusion reactions;
- If symptoms abate, re-start the infusion at one-half the previous rate;
- If symptoms do not abate after 30 minutes, discontinue the subject from the study.

Grade 4

- Administration of the agents specified for a Grade 3 infusion reaction above should be considered.
- Any subject who experiences a Grade 4 infusion reaction is to be discontinued from the study.

If a reaction with severity of Grade 2 or higher occurs upon re-challenge with KW-0761, or if in the opinion of the investigator the reaction represents a true hypersensitivity (i.e., allergic) reaction of Grade 2 or higher, KW-0761 should be stopped and not restarted and the subject should be discontinued from the study.

If an infusion reaction occurs, a serum sample should be obtained and sent to the designated central laboratory for analysis of anti-KW-0761 antibodies. (As of Amendment 10, central laboratory analysis of samples will no longer be performed [see Section 7.8].)

If an infusion reaction occurs, the duration of administration of KW-0761 should be increased to 2 hours for the next 2 infusions. Subsequent infusion duration may be 1 to 2 hours, as tolerated.

For infusion reactions occurring *after* completion of the infusion, administration of the agents specified for a Grade 3 infusion reaction above should be considered, along with any other medical intervention stipulated in institutional guidelines for the treatment of infusion reactions.

Any subject who experiences an infusion reaction requiring the administration of systemic vasopressors or that results in hospitalization (directly due to infusion reaction symptoms) of the subject is to be removed from the study.

5.2.1.8 Treatment Emergent Skin Rash

In the event a subject develops a treatment emergent skin rash, the following measures must be taken to appropriately document the event.

Patients should be closely monitored for symptoms or signs that suggest SJS or TEN. If they occur, mogamulizumab should be interrupted and treatment should not restart unless SJS or TEN is ruled out and cutaneous reaction has resolved to Grade 1 or less.

Initial Work-up of All Skin Rashes (new and re-challenge)

- 1) Notify KKD of the skin rash.
- 2) Photograph the rash. (As of Amendment 8, collection of photographs is no longer required.)
- 3) If the rash is \geq Grade 2 or if the affected area cannot be differentiated from a new area of lymphoma, a biopsy must be performed. Biopsy the rash as well as an area of skin unaffected by the rash in order to compare possible drug eruption to background lymphoma involved skin. If the rash is Grade 1 and topical steroids are to be applied, the rash must be biopsied prior to steroid treatment.
- 4) Confer with Medical Monitor or designee after completion of one week of treatment with topical corticosteroids to assess response to treatment.
- 5) Forward all results to Medical Monitor and discuss with Medical Monitor or designee a treatment plan and medical follow up.
- 6) Biopsy should be read by the dermatopathologist at the study center. Additional sample should be sent to the laboratory designated by the Sponsor for central review as well. Specific instructions for sample preparation and handling for central laboratory will be provided in the Laboratory Manual. (As of Amendment 10, central laboratory analysis of samples will no longer be performed [see Section 7.8].)
- 7) If biopsy indicates that rash is a drug eruption record appropriately as AE/SAE. If biopsy indicates that rash is lymphoma, do not record as an AE.

Rash Treatment Guidelines (after initial work-up):

Grade 1 Rash (drug related or non-drug related)

- 1) Treatment with KW-0761 may continue.
- 2) Treat rash with topical corticosteroids as needed.

Grade 2 or above Rash (drug related)

- 1) Treatment with KW-0761 must be stopped.
- 2) Treat rash with 2-week course of topical corticosteroids.
- 3) After 2-week course, re-assess rash per the steps outlined in initial assessment; if resolved completely or to Grade 1, KW-0761 treatment may be resumed. If not resolved, contact the Medical Monitor for further discussion.

Grade 2 or above rash on Re-challenge

- 1) If rash recurs and becomes a Grade 3, the subject must be discontinued from the trial and the rash work up above must be completed.
- 2) If the rash recurs at a Grade 2, follow the steps above for Grade 2 Rash.
- 3) If the rash recurs at Grade 2 or higher for a third time, the rash work up must be performed and the subject must be discontinued from the trial.

Table 5.2.1-1 Guidelines for Treatment of Skin Rash

Rash Grade	Photographs	Biopsy	Medical Monitor or designee Consult	Treatment Regimen	KW-0761	Study Participation
Initial Drug Rash						
1	Yes	Required if topical steroids will be used	Yes	Topical corticosteroids as needed	Continue	Continue
2	Yes	Yes	Yes	2-week topical steroid	Temporarily Stop; re-start if \leq Grade 1 within 2 weeks	If rash does not resolve to \leq Grade 1 within 2 weeks consult with medical monitor
3 ^a	Yes	Yes	Yes	2-week topical steroid	Temporarily Stop; re-start if \leq Grade 1 within 2 weeks	If rash does not resolve to \leq Grade 1 within 2 weeks consult with medical monitor
Subsequent Drug Rash/Rechallenge						
1	Yes	Yes	Yes	Topical corticosteroids as needed	Continue	Continue
2	Yes	Yes	Yes	2-week topical steroid	Temporarily Stop; re-start if \leq Grade 1 within 2 weeks	D/C if rash does not resolve to \leq Grade 1 within 2 weeks
3	Yes	Yes	Yes	2-week topical steroid	Discontinue	Discontinue

a Patients should be closely monitored for symptoms or signs that suggest SJS or TEN. If they occur, mogamulizumab should be interrupted and treatment should not restart unless SJS or TEN is ruled out and cutaneous reaction has resolved to Grade 1 or less.

Subjects who require systemic steroid therapy to treat a severe skin rash including SJS/TEN should be discontinued from the study.

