5.5 Criteria for Removal from Study

In the absence of a medical contraindication or significant protocol violation, every effort will be made by the Principal Investigator to keep the subject in the study. However, should the subject decide to discontinue treatment, all efforts will be made to complete and report the observations as thoroughly as possible, including a complete final evaluation at the time of the subject's withdrawal with an explanation of why the subject is withdrawing from the study.

Study treatment will be stopped if any of the following events occur:

- Disease progression (as defined in Section 7.2.4);
- An infusion-related reaction (see Section 5.2.1.7);
 - with a severity of \geq Grade 2 upon re-challenge with KW-0761,
 - with a severity of Grade 3 with symptoms that do not abate after 30 minutes,
 - with a severity of Grade 4,
 - requiring the administration of systemic vasopressors,
 - that results in hospitalization (directly due to infusion reaction symptoms),
- Initiation of treatment with systemic corticosteroids, except when initiated to treat an infusion reaction (see Section 5.2.1.7);
- A true hypersensitivity (i.e., allergic) reaction to KW-0761 with a severity of \geq Grade 2;
- A rash which recurs and becomes Grade 3 on re-challenge (see Section 5.2.1.8);
- A rash which recurs at Grade 2 or higher for a third time on re-challenge (see Section 5.2.1.8);
- A rash which requires systemic steroid therapy (see Section 5.2.1.8);
- Confirmed SJS/TEN (see Section 5.2.1.8);
- The subject has any clinical AE, laboratory abnormality, intercurrent illness, or other medical condition that indicates to the Investigator that continued participation is not in the best interest of the subject. The Investigator should make a distinction between AEs that may require only interruption of study medication and those that require discontinuation;
- The subject wishes to withdraw consent from the study in the absence of a medical need to withdraw as determined by the Investigator;
- The Investigator concludes that it is in the best interest of the subject to discontinue study treatment including subjects who have not benefited from treatment;
- Subject is willingly or inadvertently noncompliant in the opinion of the Investigator;
- Administrative reasons determined by the Sponsor; or

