7.5 Follow-Up

All subjects will be contacted by telephone every 30 days (± 7 days) up to 90 days after the last dose of study medication or initiation of alternative therapy, whichever comes first, to confirm any new onset AEs or toxicities. If a subject who has received KW-0761 undergoes a stem cell transplant at any time during or after the 90-day follow-up period, AEs/SAEs should be documented from the transplant procedure through 180 days post-transplant.

During follow-up, medications used to treat an AE and those that are temporally associated with the AE and may have a causal relationship will be recorded. In all subjects who cross

over from vorinostat to KW-0761, the causality should be assessed for both drugs for 30 days after vorinostat was stopped (or later if the event is considered to be related to vorinostat).

- After a subject who receives KW-0761 goes off study, if CD4 and CD8 counts are less than $200/\text{mm}^3$ at the End-of-treatment visit, they will be followed every 3 months (± 14 days) until they return to at least $200/\text{mm}^3$, initiation of alternative therapy or 1 year, whichever comes first.
- In the absence of disease progression, all subjects or their referring physicians will be contacted every 3 months (± 14 days) until documented disease progression or death, or initiation of alternative therapy.
- All subjects or their referring physician will be contacted every 3 months (± 14 days) to ascertain survival status.
- For all subjects who have received KW-0761, subsequent stem cell transplant information should be recorded in a separate CRF provided by the Sponsor. For subjects who undergo transplant, concomitant medications and AEs/SAEs should be documented through 180 days post-transplant on the CRFs provided.
- All follow up information and attempts to obtain follow up information should be documented in the subject's source record.

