10.3 Analyses of Efficacy Data

Disease status will be assessed every 4 weeks in skin and blood. In the first year of treatment, response in lymph nodes and viscera and the overall global composite score will be documented every 8 weeks. After the first year, response in the lymph nodes and viscera and the overall global composite score will be documented every 16 weeks. Additionally, if clinical progression is noted, efficacy assessments are performed to fully document disease progression.

These assessments will be compared with the baseline assessment to determine response. Subjects will be evaluated for response in each compartment. Progressive-free survival, overall response, duration of response, and QoL will be analyzed. For any time-to-event endpoints, the date of disease progression will be determined by both the on-site investigator's assessment and the IR. All efficacy analyses will be conducted on both the ITT and Efficacy Evaluable sets.

The primary comparison of PFS between both arms will be performed on the ITT set based upon the results of the on-site investigator's assessment using a stratified Log-rank test at the one-sided 2.5% significance level. Stratification is done by disease type, either SS or MF, and disease stage, either IB/II or III/ IV. A similar secondary analysis will be performed on the results based on the IR. Each analysis will also be conducted for the Efficacy Evaluable Set. Progressive-free survival, which will be analyzed using Kaplan-Meier survival analysis methods, is defined as the time from the day of randomization to a treatment arm until documented progression or death. For subjects who exhibit conditions of disease progression, but continue on the study due to a questionable clinical impression as described in Sections [5.2.1.4](#) and [5.2.2.3](#), the subject is not considered to have progressed unless disease

progression is confirmed at least 4 weeks after the date of the initial questionable disease progression. In this case, the initial date will be used as the date of disease progression.

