Comparisons between treatment arms for all other secondary endpoints such as Likert scale, and Itchy QoL will be conducted with no adjustment for multiple comparisons used for those statistical tests. Exploratory subset analyses for PFS and any of the secondary endpoints by region, study site, compartment involvement, CCR4 expression status, disease subtypes, and medical history may be conducted. Details of such subset analyses will be provided in the Statistical Analysis Plan. Although overall survival (OS) is not a secondary endpoint, each subject will be followed in this study for a minimum of 2 years to generate information on OS. Using this follow-up information, a comparison between treatment arms for OS will also be conducted and considered exploratory. Statistical analyses on OS using follow-up data may take place after database lock for the study and will be reported as supplemental to the Clinical Study Report.

Randomization will be stratified within the 2 disease types, SS and MF and 2 disease stages IB or II and III or IV. The efficacy analyses described in this section will be conducted as stratified tests but may also be conducted as a subset analysis within each of these disease-type groups and disease stages. Comparison of endpoints between these 2 groups and

stages will be conducted for each treatment assuming adequate sample sizes in the respective groups.

Exploratory analyses based on other subject groupings and with other parameters may also be conducted.

Since the primary endpoint is PFS, the reference median PFS for vorinostat is assumed to be 169 days. The median PFS for KW-0761 therapy is targeted for 254 days, a 50% improvement over this reference median. For a 24-month accrual and 12 month follow-up on the last subject dosed, [Table 10.3-1](#) gives the power and the number of PFS events required to show superior PFS for KW-0761 therapy over vorinostat at the one-sided 0.025 significance level. The ITT set is used for this primary analysis. The same analysis conducted using the Efficacy Evaluable set is considered secondary.

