6.11.1.1 Definition of Primary Efficacy Variable

The primary efficacy variable is progression-free survival (PFS) based upon the assessment by the Investigator, defined as the time from the day of randomization to a treatment arm until documented progression or death due to any cause.

Documented disease progression includes disease progression in any compartment based on the Investigator's assessment per CTCL response criteria or documented disease progression reported during the follow-up period. The date of progression will be the earliest date at which documented disease progression can be declared.

For subjects who exhibit conditions of disease progression, but continue on the study due to a questionable clinical impression as described in Section 3.2.2.3, the subject is not considered to have progressed unless disease progression is confirmed at least 4 weeks after the date of the initial questionable disease progression. In this case, the initial date will be used as the date of disease progression.

Subjects who died without a reported prior progression will be considered to have progressed on the day of their death.

The definition of censoring date will be as follows:

- In the event that a randomized subject withdraws from the study for any reason before documented progression, the time from the day of randomization to the last post-baseline tumor assessment from any compartment (skin, blood, bone marrow, lymph node, and viscera) will be used as a censored time point.
- For subjects who are randomized to a treatment arm but have an unknown baseline assessment for a compartment, the PFS time will be censored at the randomization date if there is no post-baseline tumor assessment for that compartment or if there is any evidence of lymphoma in that compartment at post-baseline evaluation.

- For subjects randomized to a treatment arm but withdrawing prior to the first post-baseline tumor assessment for any reason other than disease progression, the PFS time will be censored at the last documented visit.
- For subjects who initiate a new anticancer therapy (including crossover to KW-0761) in the absence of a PFS event, the PFS time will be censored at the last tumor assessment (from any compartment) prior to the start of the new anticancer therapy.

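### Terminal infusion-reaction and rash rules take the subject off the study, while section 5.5 stops only treatment, so a toxicity stop can become PFS censoring

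*Protocol*

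**What the plan says.** Protocol 5.2.1.7 ends the subject's participation after certain infusion reactions. For a Grade 3 reaction the instruction is "If symptoms do not abate after 30 minutes, discontinue the subject from the study". For a reaction on re-challenge or a true hypersensitivity reaction, one sentence orders two things: that KW-0761 stop for good, and that the subject leave the study.

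Protocol 5.2.1.8 does the same for recurrent rash ("the rash work up must be performed and the subject must be discontinued from the trial"), and the note to Table 5.2.1-1 adds "Subjects who require systemic steroid therapy to treat a severe skin rash including SJS/TEN should be discontinued from the study". Section 5.4.2 repeats the steroid rule. The table has one column for KW-0761 and a separate one for study participation; for a Grade 3 rash on re-challenge both say to discontinue.

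Section 5.5 carries removal from study in its heading, but its operative line is "Study treatment will be stopped if any of the following events occur", and the list beneath it cites 5.2.1.7 and 5.2.1.8. Section 7.5 then provides that "In the absence of disease progression, all subjects or their referring physicians will be contacted every 3 months" until progression, death or alternative therapy, and that all subjects are contacted for survival. The footnotes to Tables 1 to 3 say the same of subjects who stop for reasons other than progression.

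SAP 6.11.1.1 has a censoring rule that begins "In the event that a randomized subject withdraws from the study for any reason before documented progression" and puts the censoring time at the last post-baseline tumor assessment.

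**The concern.** Stopping a drug and leaving a study are different acts, and for the primary endpoint the difference decides whether a later progression or death is seen. The protocol gives both consequences for the same events. A site that reads 5.2.1.7 or the participation column literally will close the subject. A site that works from 5.5, 7.5 and the footnotes will keep calling. The first subject falls under the SAP withdrawal rule and is censored; the second can still contribute an event.

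Subjects leaving for severe toxicity are unlikely to be a random sample of those at risk, and they have just lost their study drug. If their hazard of progression then differs from that of comparable subjects still on treatment, the censoring is informative. The trial is open-label and the primary endpoint is investigator-assessed PFS, so the handling of these subjects should not depend on which section a site reads.

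**Working it through.** **1. The passages side by side**

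| Event | 5.2.1.7, 5.2.1.8, 5.4.2 | 5.5 |
|---|---|---|
| Infusion reaction: Grade 3 not abating; Grade 4 | off study | treatment stops |
| Infusion reaction Grade 2 or higher on re-challenge; true hypersensitivity Grade 2 or higher | drug stopped and off study | treatment stops |
| Infusion reaction needing vasopressors or causing hospitalization | removed from study | treatment stops |
| Rash: Grade 3 on re-challenge; third recurrence at Grade 2 or higher | off trial | treatment stops |
| Rash needing systemic steroids | off study | treatment stops |

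The table also has a discontinue entry under participation for a recurrent Grade 2 rash that has not settled in 2 weeks; 5.5 has no matching item.

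**2. The link to the analysis.** SAP 6.11.1.1 counts progression reported in follow-up, and death from any cause, as events. Both need the subject to be followed. No SAP sentence says that a protocol-directed stop is not withdrawal. None of the three sensitivity analyses in SAP 6.11.2.2 tests this: the first censors progression reported in follow-up, the second adds clinical progression at end of treatment, and the third concerns progression not confirmed by independent review. Only time to treatment failure, which is exploratory, counts discontinuation.

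**3. The plan's own figure.** Inputs from Protocol 10.3: "stratified Log-rank test at the one-sided 2.5% significance level"; "the reference median PFS for vorinostat is assumed to be 169 days"; KW-0761 median 254 days; 24 months of accrual plus 12 of follow-up. Allocation is 1:1.

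- HR = 169/254 = 0.665; ln HR = -0.407.
- Schoenfeld: d = 4(1.960 + 1.282)²/0.407² = 254 events (plan: 255). Power at 255 events is 90.2%.
- Event probability by 36 months: P = 1 - [exp(-λF) - exp(-λ(A+F))]/(λA), with λ = ln 2/median, A = 730.5 days and F = 365.25 days. This gives 0.929 for vorinostat and 0.840 for KW-0761. With N = 288: 144 × (0.929 + 0.840) = 254.8 events.

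The design reproduces.

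**4. Events lost.** The documents give no removal rate, so it is assumed. Add a competing exponential removal to the KW-0761 arm, with its rate c set so that a fraction f of the arm is removed before progression by the 36-month cut, and treat the censoring as non-informative:

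| f | Events, N = 288 | Power | Events, N = 317 |
|---|---|---|---|
| 5% | 249.8 | 89.6% | 275.0 |
| 10% | 244.8 | 89.0% | 269.5 |
| 20% | 234.6 | 87.7% | 258.2 |
| 25% | 229.3 | 87.0% | 252.4 |

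In an event-driven trial most of this becomes delay.

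**5. Bias.** Let the hazard after removal be k times the KW-0761 on-drug hazard. For scale, 254/169 = 1.5, so k = 1.5 means falling back to the planned vorinostat hazard. Cox estimates, simulated with 400,000 per arm:

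| f | k | HR, followed | HR, censored | Difference |
|---|---|---|---|---|
| 10% | 1 | 0.666 | 0.666 | 0 |
| 10% | 1.5 | 0.686 | 0.666 | 0.020 |
| 10% | 2 | 0.696 | 0.664 | 0.032 |
| 20% | 1 | 0.663 | 0.663 | 0 |
| 20% | 1.5 | 0.708 | 0.668 | 0.040 |
| 20% | 2 | 0.736 | 0.667 | 0.069 |

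With N = 288 these fractions mean 0.10 × 144 = 14 to 0.20 × 144 = 29 subjects. The model changes the KW-0761 arm only, and its followed column assumes that every later progression is observed.

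**The case against.** The best reply is that the protocol uses leaving the study loosely, to mean the end of treatment. Section 5.2.1.4 ties the end of the treatment phase to the study-removal criteria of 5.5, and 5.5 only stops treatment. Section 7.5 speaks of KW-0761 subjects going off study and in the same sentence schedules further CD4 and CD8 checks. The SAP disposition shell (Table 14.1.1.1) lists adverse events as a reason for stopping drug but not for leaving the study. And the primary definition already counts progression reported in follow-up.

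This is good evidence of what the sponsor meant, and it is why the point is a reconciliation rather than a design error. It does not settle what a site will do. The re-challenge sentence in 5.2.1.7 and the two table columns keep drug and participation apart, and both end. Section 5.2.1.4 also exempts unacceptable toxicity and drug intolerance from the effort to keep subjects in the study until progression.

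Two other parts of the reply stand. Follow-up under 7.5 is by contact every 3 months, with no scheduled tumor assessments after a toxicity stop (those in 7.6 are for complete responders), and it ends at alternative therapy, where the SAP censors in any case. So the followed column above overstates what better wording would recover. And the removal rates and hazard multipliers are assumptions.

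**Conclusion.** The contradiction is in the text, and it reaches the primary endpoint through SAP 6.11.1.1. It can produce informative censoring; the documents do not show that it does, or how often. Under 10-20% removal in the KW-0761 arm and a post-stop hazard 1.5-2 times higher, the PFS hazard ratio would read about 0.02-0.07 too low. With an unchanged hazard there is no bias, and the power cost is about 1 to 3 points for 10-25% removal.

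Three stronger readings are tempting and are not supported:

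- **That the rules favour KW-0761.** The calculation models one arm. Under Protocol 5.3, vorinostat-intolerant subjects may cross over without progression, and the SAP then censors them. That is toxicity-related censoring in the other arm, so the net direction is open. The steroid rule in 5.4.2 names no arm.
- **That survival data are lost.** Section 7.5 requires survival contact for all subjects. Data would be lost only where a site closes the subject. OS is exploratory, and crossed-over subjects come under the KW-0761 rules too.
- **That any Grade 3 infusion reaction means exit.** One that abates allows the infusion to restart; exit needs failure to abate or another listed trigger.

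The repair is worth making because it is cheap and removes a choice that should not rest with each site.

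**What to change.** Reconcile 5.2.1.7, 5.2.1.8, Table 5.2.1-1 and 5.4.2 with 5.5 and 7.5, so that stopping drug and leaving the study are named as separate acts and the follow-up status under 7.5 is stated for each event. Include the table's recurrent Grade 2 entry, which 5.5 does not mention. No drug-stopping criterion need change, and none is judged here.

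Add one sentence to SAP 6.11.1.1: a treatment stop directed by the protocol is not withdrawal from the study, so progression or death documented afterwards, and before any new anticancer therapy, counts as a PFS event.

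The cost is amendment wording, one SAP sentence and a few more follow-up contacts, which 7.5 already requires. Because follow-up is by contact and ends at alternative therapy, the change recovers some of the events, not all.
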